The t_{max} and $t_{1/2}$ for ASLAN003 were dose-independent following QD doses across the selected dose range; 5 and 16 hours, respectively. Steady-state concentrations of ASLAN003, LAS186558, and LAS186876 were achieved by Day 4 across the selected dose range. Following daily repeated dosing, exposure to ASLAN003 and LAS186558 (AUC) appeared to accumulate slightly (less than 30% increase). The exposure was higher in elderly subjects (AUC_{tau}) of ASLAN003 was increased by 53% and C_{max} by 41%), which may be explained by their lower body weight. Renal elimination of free (unconjugated) ASLAN003, LAS186558, and LAS186876 were negligible (<0.8% of the administered dose). Phase II metabolism appeared to be an important route of elimination. Conjugation was most prevalent for ASLAN003 and LAS186558.

Most frequently reported adverse events (AEs) across this ASLAN003-001 study were abnormality in laboratory investigations and included elevated alanine aminotransferase (ALT), aspartate aminotransferase (AST), gamma glutamyltransferase, blood cholesterol increased, blood creatine phosphokinase increased, electrocardiogram (ECG) PR, and blood glucose increased. The safety assessment results reported in patients aged ≥ 55 years were mostly comparable with those of younger subjects other than for greater changes in the laboratory assessments in the elderly subjects compared to the younger subjects, notably the liver function tests.

Another Phase IB study (*Study ASLAN003-002*) evaluated the safety, tolerability and PKs of multiple doses of 100 mg of ASLAN003 QD for 14 days in healthy elderly Asian subjects (age > 55 years old). The study was conducted at a single center in Singapore where 7 of the planned 8 elderly subjects were enrolled into Stage 1 of the study, of which

5 subjects received ASLAN 100 mg QD on Day 1; and 4 of these subjects received ASLAN 100 mg QD on Day 8. Only 1 subject completed 14 days of QD dosing. Stage 2 of the study was not conducted. Following daily repeated dosing, mean plasma exposure to ASLAN003 expressed as $AUC_{(0-24)}$ increased 1.2-fold after multiple dosing on Day 8 compared to a single dose on Day 1. Following repeat QD dosing, the relative systemic exposures to the metabolites LAS186558 and LAS186876 were around 10% and 1%, respectively.

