6.4 Pharmacokinetics Assessment (Part 1 ONLY)

The blood samples for determination of ASLAN003 and metabolite concentrations will be collected on Day 1 and Day 8 Cycle 1 in Table 4 at the following timepoints:

Table 4: ASLAN003 Pharmacokinetic Assessment Schedule

Scheduled Visit	Time Points (h)	PK Parameters
Day 1	Pre-dose	C_{max} , $C_{max\ ss}$, C_{trough} , t_{max} , AUC_{τ} , $t_{1/2}$, $t_{1/2\ eff}$, Cl/F^* & V_{ss}/F^*
	Post dose: at 1, 2, 4, 5, 6, 8, 12#, and 24 hours	
Day 8	Pre-dose	$C_{max\ ss}$, C_{trough} , $t_{max\ ss}$, $AUC_{\tau\ ss}$, Cl/F^* , $t_{1/2}$, $t_{1/2\ eff}$, $MRAUC^{**}$, MRC_{max}^{**} , $RacAUC$, and $RacC_{max}$
	Post dose: at 1, 2, 4, 5, 6, 8, 12#, and 24 hours	

Note: Only ASLAN003 and its metabolite's (LAS186558) concentrations and PK parameters will be determined in this study.

* Parameter calculated only for ASLAN003

** Parameter calculated only for LAS186558

Sample collected for BID regime only.

Abbreviations: AUC = area under the plasma concentration curve; AUC_{τ} = AUC over the dosing interval; $AUC_{\tau\ ss}$ = AUC_{τ} at steady state; Cl/F = apparent total clearance of the drug from plasma after oral administration at steady state; C_{max} = maximum observed plasma concentration; $C_{max\ ss}$ = C_{max} at steady state; C_{trough} = Trough plasma concentration; $RacAUC$ = accumulation ratio for AUC; $RacC_{max}$ = accumulation ratio for C_{max} ; t_{max} = time corresponding to occurrence of C_{max} ; $t_{max\ ss}$ = time corresponding to occurrence of $C_{max\ ss}$; MR = metabolic ratio; $MRAUC$ = metabolic ratio for AUC; MRC_{max} = metabolic ratio for C_{max} ; $t_{1/2}$ = effective elimination half-life; $t_{1/2\ eff}$ = effective elimination half-life at the steady state; V_{ss}/F = apparent volume of distribution at steady state after oral administration

In BID regime i.e 100mg BID and 200mg BID the PK sampling will be done at following timepoints: pre-dose, 1, 2, 4, 5, 6, 8, and 12 hours (or evening pre-dose). For Part 2- Steering Committee will decide whether PK analysis is required or not and ASLAN pharmaceuticals will be updated accordingly

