- $t_{1/2}$ Terminal elimination half-life (h). Visual assessment will be used to identify the terminal linear phase of the concentration-time profile

- MR Metabolite to parent ratio (LAS186558 to ASLAN003) for AUC_{τ} and C_{\max} ($MRAUC_{\tau}$ and MRC_{\max})
- C_{\max}/D Dose-normalized C_{\max} (ng/mL/mg).
- AUC_{last}/D Dose-normalized AUC_{last} (ng.h/mL/mg).
- AUC_{τ}/D Dose-normalized AUC_{τ} (ng.h/mL/mg).

The following PK parameters will be calculated for ASLAN003 and LAS186558 for diagnostic purposes and listed but not summarized:

- λ_z , Interval The time interval (h) of the log-linear regression to determine $t_{1/2}$
- λ_z , N Number of data points included in the log-linear regression analysis
- Rsq(adj) Coefficient of determination for calculation of λ_z . A value of >0.800 is indicative of good correlation and will be used as the criteria for reliable estimations of λ_z , $t_{1/2}$, and related parameters will not be reported if Rsq(adj) is ≤ 0.8
- %AUC Percentage of AUC obtained by extrapolation, calculated as $[(C_{\text{last}}/\lambda_z)/AUC_{\text{inf}}*100]$. If value is $>20\%$, AUC_{inf} , CL/F , and V_z/F will be listed but not included in any summaries or inferential analyses.

Where possible the following PK parameters will be determined for ASLAN003 and LAS186558 following multiple dosing on Day 8.

- $AUC_{\tau \text{ ss}}$ Area under the plasma concentration-time curve during the dosing interval, tau, (ng*h/mL), calculated by linear up/log down trapezoidal summation
- $C_{\max \text{ ss}}$ Maximum plasma concentration (ng/mL) obtained directly from the observed concentration versus time data
- $t_{\max \text{ ss}}$ Time to maximum plasma concentration (h) obtained directly from the observed concentration versus time data
- $AUC_{\text{last ss}}$ Area under the plasma concentration-time curve from 0 to the time of the last quantifiable concentration (ng*h/mL), calculated by linear up/log down trapezoidal summation

- C_{trough} Plasma concentration obtained prior to dosing on Day 8
- $t_{1/2 \text{ eff}}$ Effective elimination half-life at steady state calculated as
 $\ln 2 / \text{Lambda}_z \text{ (eff)} = [-\ln 2 * \tau / \ln \{1 - [AUC_{\tau, \text{ Day 1}} / AUC_{\tau, \text{ Day 8}}]\}]$ with
 $\tau = 24$ hours for QD dosing and 12 hours for BID dosing
- CL_{ss}/F Apparent plasma clearance for ASLAN003 only (L/h), estimated as dose divided by $AUC_{\tau \text{ ss}}$

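### Effective half-life is summarised only in patients whose AUC rises from Day 1 to Day 8, which can bias the QD summary long; BID terminal half-life rests on too short a window for the R-squared gate to protect it

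*SAP*

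**What the plan says.** **Effective half-life.** SAP 7.11 defines it for Day 8: "Effective elimination half-life at steady state calculated as" -ln2 × tau / ln(1 - AUCtau Day 1 / AUCtau Day 8), with tau equal to 24 "hours for QD dosing and 12 hours for BID dosing". Day 8 parameters are derived only as far as the data allow. SAP 6.3 leaves missing values missing and out of the analyses. Nothing is said about a patient whose Day 8 AUC is equal to or below the Day 1 AUC.

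**Terminal half-life.** Also in SAP 7.11: "Visual assessment will be used to identify the terminal linear phase of the concentration-time profile". The only numerical gate is adjusted R-squared: "A value of >0.800 is indicative of good correlation and will be used as the criteria for reliable estimations of" the terminal rate constant, "and related parameters will not be reported if Rsq(adj) is" 0.8 or lower. No minimum time span is set. The 20% extrapolation rule takes AUCinf, CL/F and Vz/F out of the summaries but not the half-life.

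**Sampling and prior data.** QD profiles run to 24 h. BID sampling in Protocol 6.4 is "pre-dose, 1, 2, 4, 5, 6, 8, and 12 hours (or evening pre-dose". Table 4 in the same section marks only the 12 h sample as BID-only, which leaves a 24 h BID sample unclear, but the text below the table and the other sampling descriptions end BID profiles at 12 h. Protocol 1.4 gives tmax and half-life in healthy subjects as "dose-independent following QD doses across the selected dose range; 5 and 16 hours, respectively". It says that exposure to the drug and to LAS186558 "appeared to accumulate slightly (less than 30% increase", and it reports a 1.2-fold rise by Day 8 in the elderly study.

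**The concern.** Both half-lives are summarised only in patients whose data return a value, and whether they do depends on the quantity being estimated.

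For effective half-life, the patients lost are those with the lowest observed accumulation, so those who remain read long. The loss is uneven between regimens. QD accumulation is expected to lie just above 1, the point at which the formula fails. The same half-life under BID dosing gives a ratio well clear of 1. Two cohorts with identical kinetics could therefore show different effective half-lives.

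For terminal half-life, a fit to three points over a short interval passes the R-squared gate more easily when error makes the slope look steep. PK is the secondary objective of Part 1 and the steering committee reviews PK data, so a reader may well set the QD and BID columns side by side.

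**Working it through.** The plan states no figure for this point, so there is none to reproduce. The documents give no within-patient AUC CV and no residual error for concentrations. Both are assumed below and shown over a range.

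**1. What the stated figures imply.** With accumulation ratio R = AUCtau Day 8 / AUCtau Day 1, the SAP formula at tau = 24 h gives:
- R = 1.2: -0.693 × 24 / ln(1 - 1/1.2) = 9.3 h.
- R = 1.3: 11.3 h.

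The inverse is R = 1 / (1 - exp(-ln2 × tau / t½)). A half-life of 9.3 h gives R = 1.69 under BID, and 11.3 h gives 1.92. A half-life of 16 h would give R = 1.55 under QD, so the stated 16 h and the stated accumulation do not fit a one-compartment model. Effective and terminal half-life must be judged separately.

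**2. Effective half-life.** Take log R as normal with mean ln(true R) and SD s = sqrt(2 × ln(1 + CV²)), from two independent AUCs.
- P(undefined) = P(R ≤ 1) = Φ(-ln(true R) / s).
- The median R among those retained is the quantile of R at P + (1 - P)/2, put through the SAP formula.

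Example, QD, true R = 1.2, CV 20%: s = 0.280, so P = Φ(-0.182/0.280) = Φ(-0.651) = 0.26. The retained median R is 1.316, which gives 11.65 h.

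| AUC CV (assumed) | QD undefined | QD median, true 9.28 h | BID undefined | BID median, true 9.28 h |
|---|---|---|---|---|
| 5% | 0.5% | 9.30 h | 0% | 9.28 h |
| 10% | 10% | 9.73 h | <0.1% | 9.28 h |
| 20% | 26% | 11.65 h | 3% | 9.45 h |
| 30% | 33% | 13.89 h | 10% | 10.11 h |

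In a cohort of six at CV 20%, the chance that at least one QD patient is undefined is 1 - (1 - 0.2575)^6 = 0.83. At true R = 1.3 (11.3 h) the effect is smaller: QD medians are 11.5, 12.9 and 15.1 h at CV 10, 20 and 30%.

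**3. Terminal half-life.** After a 5 h peak, the BID samples are 6, 8 and 12 h: three points over 6 h, and 6/16 = 0.4 of the stated half-life. QD has 6, 8 and 24 h, a span of 18 h. The next table simulates a one-compartment oral model (half-life 16 h, tmax 5 h), keeping fits with a negative slope and adjusted R-squared above 0.8.

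| Concentration CV (assumed) | QD reported, median | BID reported, median |
|---|---|---|
| 2% | 100%, 16.8 h | 97%, 19.1 h |
| 5% | 100%, 16.8 h | 67%, 17.9 h |
| 10% | 93%, 16.7 h | 38%, 14.5 h |
| 20% | 64%, 15.5 h | 23%, 9.7 h |

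BID reads long at low error, because absorption still flattens the 6 to 12 h segment, and short at 10% or more. A two-phase model, calibrated to a 16 h terminal phase and R of 1.2 to 1.3, gives noise-free values of 7.1 to 8.4 h for QD and 8.6 to 9.6 h for BID. Both are short, and BID falls below QD only at a CV of about 20% or more.

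**4. Cohort-level alternative.** Apply the formula once to the geometric mean of R over six patients (true 9.28 h). At CV 10, 20 and 30% the median QD result is 9.3, 9.5 and 10.0 h, and BID is 9.3 h throughout. The QD geometric mean is at or below 1 in about 0.1, 6 and 14% of cohorts.

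**The case against.** A reader might infer that the plan will necessarily manufacture a regimen difference, with BID terminal half-life short and QD effective half-life long. The documents do not support that. The effective half-life bias needs an AUC CV of about 10% or more, which they neither give nor rule out; at 5% there is none. For terminal half-life even the sign changes with the error size and the PK model.

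A reader might also infer that half-life is the basis for moving from QD to BID. It is not. Protocol 1.6 rests the BID cohorts on an observed trough below the enzyme IC50 and on a simulation model. Protocol 6.1 and 8.4.2 rest the optimum dose on efficacy and tolerability. No formal analysis is planned, and the PK plots against dose in SAP section 6 cover dose-normalised AUC and Cmax, not half-life.

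The plan also has safeguards. Protocol 3.3.2 makes these parameters conditional on being estimable. The accumulation ratio is itself summarised with a geometric mean and is defined at ratios of 1 or less. N and n are both shown, and the regression interval and number of points are listed for each profile.

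These points limit the consequence. They do not remove the fault in the effective half-life summary: n shows that patients were lost but not that they were the low-accumulation ones, and the table would still print the selected median. Nor do they make three points over 6 h an adequate basis for summarising a half-life near 16 h.

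**Conclusion.** The point holds for effective half-life. As written, the QD summary excludes patients whose AUC does not rise from Day 1 to Day 8, and at the accumulation the protocol reports this can bias it long. With a true 9.3 h, the median error is nil at CV 5%, about 0.4 h at 10%, 2.4 h at 20% and 4.6 h at 30%, while BID moves by at most 0.8 h. This rests on the assumed CV, log-normal independent AUC errors, and accumulation of 1.2-fold as in the healthy elderly subjects of Protocol 1.4.

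For terminal half-life the conclusion is narrower: the BID value is unreliable and the R-squared gate does not change that, but neither the size nor the direction of the error can be fixed from the documents. Any QD-versus-BID difference in either half-life should be read as a possible artefact. The consequence is for description and interpretation only. The change is worth making because it is cheap.

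**What to change.** In SAP 7.11:

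1. Derive the summary effective half-life once per cohort from the geometric mean accumulation ratio over all patients with both AUCtau values, including ratios of 1 or less. Take a confidence interval from the log ratios and transform its limits. Report not estimable where the geometric mean or a limit is 1 or less. List individual values only, with the number undefined.
2. Make terminal half-life and the terminal rate constant listing-only for the BID cohorts, by regimen, because of the fixed 12 h sampling window.
3. Do not compare terminal half-life between QD and BID.

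Do not add a rule that the regression interval must span one estimated half-life. It selects on the outcome: QD could keep only estimates up to 18 h and BID only up to 6 h. In a pure-exponential simulation with a true 16 h, that rule moves the QD median from 15.9 to 15.2 h at 10% error and from 15.5 to 14.3 h at 15%. The rare BID profiles that pass have a median of about 5.5 h.

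The cost is SAP wording and a few lines of code. What is lost is a BID summary of terminal half-life and an individual-level summary of effective half-life. The cohort interval will often be open at the lower end. With six patients, R = 1.2 and CV 20%, a 95% interval for R is typically 1.2 × exp(±2.571 × 0.280/√6) = 0.89 to 1.61, so the lower limit for half-life is not estimable. That is a fair statement of what six patients can show.

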7.11.1 Concentration Values

All concentration values below the lower limit of quantification (LLQ) and samples with no reportable value occurring prior to dosing will be replaced by "0". For tabulation, graphical representation and calculation of summary statistics, all samples <LLQ or with no reportable value observed after the drug administration will be treated as missing.

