4.4 PK Analysis Set

The PK population contains all patients who have received one complete dose of ASLAN003 and have at least one measured concentration at a scheduled post-dose time point without any major protocol deviations or events that affect the PK concentrations. Patients in this population will be used for all PK analyses.

All PK data will be analyzed according to treatment received.

This population will comprise all data from patients who receive study treatment as per protocol (e.g. 100 mg QD, 200 mg QD, 100 mg BID or 200 mg BID) and did not violate or deviate from the protocol and planned dosing regimen in ways that would significantly affect the PK analyses (for example skipping doses, or taking reduced doses or taking concomitant medications with the potential to cause a drug-drug interaction) during the PK sampling period. Patients who did deviate from the planned dosing regimen may still provide some data for inclusion in the PK set, if they have at least one usable PK profile. The population, and decisions regarding which profiles are usable, will be defined by the Study Team Physician, Pharmacokineticist and Statistician prior to any analyses being performed.

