Plasma concentrations of ASLAN003 and LAS186558 will be presented descriptively by study day and nominal time point for the PK analysis set including number of subjects (N), number of observations (n), mean, SD, coefficient of variation (CV%) median, minimum, and maximum. The below limit of quantification (BLQ) PK concentration values will be set to zero prior to computing descriptive statistics of PK concentrations. Missing concentrations will be omitted from the calculation of descriptive statistics.

Individual plasma and mean concentration-time plots will be provided using a linear and semi-logarithmic scale.

Descriptive statistics for PK parameters (see Section 7.11 for calculations) will be summarized by study day (N, n, arithmetic mean, SD of the arithmetic mean, CV%, median, minimum, maximum geometric mean [GeoMean], and geometric coefficient of variation [GeoCV%]). For t_{max} , only n, minimum, median, and maximum will be reported. For calculation and presentation of PK parameter descriptive statistics, values as presented in the data listings will be used as the source data. Minimum, maximum, mean, GeoMean, and median will be presented to the same significant figure precision as listed data. Standard deviation will be presented to 1 significant figure more than the precision of the data listed. The CV% and GeoCV% will always be reported to 1 decimal place. Derived parameters will be reported to 3 significant

figures, except for parameters that are taken directly from concentration data which will be reported using similar precision to those from which they were derived or elapsed sampling times which will be reported as 2 decimal places.

Scatter plots of individual subject and geometric mean dose-normalized AUC_{tau} (or AUC_{last}), $AUC_{tau ss}$ (or $AUC_{last ss}$), C_{max} and $C_{max ss}$ values versus dose will be presented.

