9. LIST OF TABLES, FIGURES AND LISTINGS

9.1 Tables

Unless otherwise stated, tables will be all repeated for part 1 and part 2.

Table Number	Table Title
14.1.1	Patient Disposition and Withdrawals – All Patients
14.1.2	Analysis Populations – All Patients
14.1.3.1	Major Protocol Deviations – Full Analysis Set
14.1.3.2	Other Important Protocol Deviations – Full Analysis Set
14.1.4	Demographic Characteristics – Full Analysis Set
14.1.5	Prior Therapies for AML – Full Analysis Set
14.2.1.1	Summary of Overall Complete Remission Rate – EFR Population
14.2.1.2	Summary of Overall Complete Remission Rate – Full Analysis Set
14.2.2.1	Summary Statistics for Relapse-Free Survival – EFR Population
14.2.2.2	Summary Statistics for Relapse-Free Survival – Full Analysis Set
14.2.3.1	Summary of Clinical Benefit Rate – EFR Population
14.2.3.2	Summary of Clinical Benefit Rate – Full Analysis Set
14.2.5.1	Summary of Plasma Concentrations – ASLAN003 – PK Population
14.2.5.2	Summary of Plasma Concentrations – LAS186558 – PK Population
14.2.5.3	Summary of Plasma Pharmacokinetic Parameters – ASLAN003 - PK Population
14.2.5.4	Summary of Plasma Pharmacokinetic Parameters – LAS186558 - PK Population
14.3.1.1	Summary Statistics for Exposure – Safety Population
14.3.1.2	Summary Statistics for Dose Intensity – Safety Population
14.3.2.1	Overview of TEAEs – Safety Population

Table Number	Table Title
14.3.2.2	Incidence of TEAEs by System Organ Class and Preferred Term – Patient and Episode Level – Safety Population
14.3.2.3	Incidence of Causally Related TEAEs by System Organ Class and Preferred Term – Patient and Episode Level – Safety Population
14.3.2.4	Incidence of most frequent (>10%) TEAEs by Preferred Term – Safety Population
14.3.2.5	Incidence of most frequent (>10%) Causally Related TEAEs by Preferred Term – Safety Population
14.3.2.6	Incidence of TEAEs CTCAE Grade 3 or Higher by System Organ Class and Preferred Term – Safety Population
14.3.2.7	Incidence of Causally Related TEAEs CTCAE Grade 3 or Higher by System Organ Class and Preferred Term – Safety Population
14.3.2.8	Incidence of Serious TEAEs by System Organ Class and Preferred Term – Safety Population
14.3.2.9	Incidence of Serious Causally Related TEAEs by System Organ Class and Preferred Term – Safety Population
14.3.3	Summary of Deaths – Safety Population

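### SAP Section 6 sets post-dose BLQ concentrations to zero, SAP 7.11.1 makes them missing in the same tables, and 7.11.1 also gives a zero trough for a Day 8 pre-dose sample with no result

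*SAP*

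**What the plan says.** **Concentration summaries.** The PK rules in SAP Section 6 (General Statistical Considerations) cover plasma concentrations of ASLAN003 and LAS186558, summarised by study day and nominal time. They state: "The below limit of quantification (BLQ) PK concentration values will be set to zero prior to computing descriptive statistics of PK concentrations". The next sentence adds: "Missing concentrations will be omitted from the calculation of descriptive statistics". Neither sentence separates pre-dose from post-dose samples.

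SAP 7.11.1 (Concentration Values) does separate them. Before dosing, values below the limit become zero, and "samples with no reportable value occurring prior to dosing will be replaced by" zero as well. After dosing, "all samples <LLQ or with no reportable value observed after the drug administration will be treated as missing". The scope given for this second rule is tables, graphs and summary statistics.

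The outputs concerned are Tables 14.2.5.1 (ASLAN003) and 14.2.5.2 ("Summary of Plasma Concentrations – LAS186558 – PK Population"). Both report means, SDs, CV%, medians, minima and maxima.

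**Trough.** SAP 7.11 defines C_trough as "Plasma concentration obtained prior to dosing on Day 8". It is a PK parameter, and Section 6 plans a geometric mean and geometric CV for PK parameters, but not for concentrations.

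**Missing data in general.** SAP 6.3 leaves missing data missing and keeps them out of analyses. The only exception it lists concerns baseline values.

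**The concern.** For a post-dose sample below the limit, the SAP gives two incompatible instructions for the same table cell. Two programmers could each follow the SAP and produce different results. The true value lies between zero and the quantification limit, so setting it to zero pulls the mean down, while dropping it removes the lowest observations and pushes the mean up.

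The second problem is narrower. At Day 8 a patient has had a week of dosing. A pre-dose sample that was taken but could not be reported says nothing about the trough, yet 7.11.1 would record it as zero.

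PK is the secondary objective of Part 1, with 6 patients per cohort, so a single value carries weight. Protocol 1.6 also cites the trough level at 100 mg QD as the reason for adding twice-daily cohorts.

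**Working it through.** The SAP states no figure on this point, so there is none to reproduce. The check has two parts.

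**1. The rules side by side.** Pre-dose is read per profile, that is, relative to that day's dose. Section 6 entries for samples with no result assume that no reportable value means missing, which the SAP does not say.

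| Sample | Section 6 | 7.11.1 | Agree? |
|---|---|---|---|
| BLQ, Day 1 pre-dose | 0 | 0 | Yes |
| BLQ, post-dose | 0 | Missing | **No** |
| BLQ, Day 8 pre-dose | 0 | 0 | Yes |
| No result, Day 1 pre-dose | Omitted | 0 | No, but harmless |
| No result, Day 8 pre-dose | Omitted | 0 | **No** |
| No result, post-dose | Omitted | Missing | Yes |

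The Day 1 pre-dose difference is harmless because exclusion criterion 11 bars earlier ASLAN003 treatment, so zero is the right value there.

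**2. Size of the post-dose conflict.** Inputs: n = 6 per cohort (SAP 2.1). The number of BLQ values, z, is assumed to be 1, 2 or 3.

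Mean. The sum of the quantifiable values is the same under both rules; only the divisor differs (6 or 6 − z). So Section 6 mean ÷ 7.11.1 mean = (6 − z)/6, whatever the quantifiable values are:
- z = 1: 5/6 = 0.833
- z = 2: 4/6 = 0.667
- z = 3: 3/6 = 0.5

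CV%. Let m = 6 − z quantifiable values have mean 1 and CV c. With the zeros included, the mean is m/6 and the variance is [m + (m − 1)c² − m²/6]/5.
- c = 0 (all quantifiable values identical, the lower bound), z = 1: variance = (5 − 25/6)/5 = 0.1667, SD = 0.408, CV = 0.408/0.833 = 49.0%. For z = 2 and 3 the CV is 77.5% and 109.5%. Under 7.11.1 it would be 0%.
- c = 0.3 (assumed): 58.6%, 84.9% and 115.9% for z = 1, 2 and 3, against 30% under 7.11.1.

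All statistics together, with assumed values 2, 3, 4, 6, 8, 12 and the lowest two BLQ:

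| | n | Mean | SD | CV% | Median | Minimum |
|---|---|---|---|---|---|---|
| Section 6 (zero) | 6 | 5.0 | 4.69 | 93.8 | 5 | 0 |
| 7.11.1 (missing) | 4 | 7.5 | 3.42 | 45.5 | 7 | 4 |

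**Day 8 sample with no result.** The same ratio applies to mean C_trough. One such sample entered as zero instead of omitted lowers a 6-patient mean by 1 − 5/6 = 16.7%; two lower it by 1 − 4/6 = 33.3%. Any zero also makes the geometric mean zero or undefined and the geometric CV undefined.

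**The case against.** **The effect may never arise.** Protocol 1.4 reports a t_max of 5 hours and a half-life of 16 hours for the parent drug in healthy subjects. Assuming mono-exponential decline, the level at 24 hours is 2^(−19/16), about 44% of peak, and at 12 hours 2^(−7/16), about 74%. Sampling stops there. Nothing in the documents points to parent BLQ values in 2 or 3 of 6 patients at a post-dose time. LAS186558 is the likelier analyte, at around 10% of parent exposure, but that says little without the quantification limit. This stands: the ratios above are arithmetic on assumed counts, not expected effects. It does not remove the conflict between the rules.

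**Section 6 points to 7.11.** It does, but for the calculation of PK parameters. It gives no precedence for concentration summaries, where both sections claim the same outputs. Nor can one rule be kept for parameters and the other for summaries, since both name descriptive or summary statistics.

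**Safeguards for the trough.** SAP 4.4 says "decisions regarding which profiles are usable, will be defined by the Study Team Physician, Pharmacokineticist and Statistician prior to any analyses being performed", 7.11 derives parameters only where possible, and 6.3 leaves missing data missing. A sample never drawn may also fall outside the 7.11.1 wording, which would limit the problem to samples collected but not reportable. These points lower the risk of a false zero. They do not remove it, because 7.11.1 is the more specific text and says zero.

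**A stronger reading of the trough problem.** A reader might infer that a BLQ Day 8 pre-dose value is also caught between two rules, since it follows earlier doses. The documents do not support that. C_trough is itself defined as prior to dosing on Day 8, and SAP 7.11.2 assigns time zero to pre-dose samples generally, so pre-dose belongs to each profile. A BLQ value there is zero under both sections. Only its place in the geometric statistics is open.

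**Conclusion.** The conflict over post-dose BLQ concentrations is real, and the SAP cannot be followed as written for Tables 14.2.5.1 and 14.2.5.2. Separately, 7.11.1 yields a false trough of zero when a Day 8 pre-dose sample has no reportable value, contrary to SAP 6.3.

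The size is conditional on counts that the documents do not give. The mean ratio (6 − z)/6 is exact for any z of 6; the CV figures also depend on the assumed spread.

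Severity is minor. A reader might infer that dose selection or the efficacy conclusions are at risk. The documents do not show this: no PK test or PK threshold is stated, OCRR and safety do not use these values, and individual concentrations are still listed (Listing 16.2.6.1.1).

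**What to change.** - Keep one BLQ rule for post-dose concentrations, in one place. For example, keep the Section 6 zero rule, show the number of BLQ values at each time point, and delete the conflicting sentence in 7.11.1. If the missing rule is preferred, delete the Section 6 sentence instead.
- Limit zero replacement of samples with no reportable value to Day 1 pre-dose. Treat them as missing at every other time, including Day 8 pre-dose, so that such a patient has no C_trough. Say whether no reportable value and missing mean the same.
- State that a C_trough of zero is left out of the geometric mean and geometric CV, and report how many were left out.

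The cost is SAP wording, plus a BLQ count in two existing tables and a count of excluded troughs in the parameter tables. No new data are needed. SAP 7.11 places the PK analysis after database lock, so the wording should be settled before then.
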